All the participants will be enrolled into a "whatsapp" group where they will discuss satisfaction with ART services provided to them. An expert will be involved on the group to offer counsel on issues of client satisfaction with ART services. All the participants will also receive a simple clinic-based intervention that is based on stress and coping theories and cognitive behavioural therapy which is aimed at improving their mental status.

Follow-up

The follow-up visits will hold every four weeks at 4, 8, 12, 16, and 20 weeks after the baseline to coincide with the participants' routine clinic visits. ART adherence and client satisfaction will be assessed at each follow-up visit. The participants will also receive the adherence counseling by trained counselors at each visit. CHIV viral load assessments will be done at Baseline and 20 weeks. In order to complete the study, a participant is required to attend all follow-up visits.

[figure not shown]

Figure 1: Randomized controlled study design

Adherence counseling

In this trial, the counselors will be female master's degree level social workers with ART counseling experience. The adherence counselor will be mentored and will be supervised by the investigators. Adherence counseling will be conducted in a setting that mimics a typical ART clinic setting. Each session will consist of a 15 minutes face to face session and will deliver information on the impact of HIV on the

human immune system, the role of ART, the importance of adherence, the characteristics and consequences of non-adherence, and strategies to enhance adherence. The '5As of adherence' approach will be used (38).

Trial Assistance

The trial assistants will be bachelor's degree holders in relevant disciplines and with relevant research experience. They will be trained in research ethics, the study protocol, data collection tools, and data entry. They will obtain a signed informed consent from participants and allocate unique identifiers to them. The trial assistants will also administer the questionnaires, enter data into analysis software and assist participants in getting laboratory investigations done.

Trial Coordination

This trial will be coordinated on a day-to-day basis by a coordinator who will be an MPH degree holder with relevant experience in research coordination.

EXPECTED OUTCOMES

Primary outcome measure (ART adherence)

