ART adherence will be assessed using the visual analog scale (VAS), Viral load, Pill count, Pharmacy record, and the AIDS Clinical Trials Group (ACTG) adherence questionnaires at baseline and during every follow-up visits. The VAS has been found to be reliable, valid and suited for patients in resource-limited settings with insufficient human resources for time-consuming adherence assessments. It showed the highest sensitivity to detect patients with possible virologic failure at 95% cut-off for non-adherence (1, 39).

Secondary outcome measures

1. Patient satisfaction

Patient satisfaction is a potent predictor of ART adherence (40, 41).

2. Mental health status

Mental illnesses are varied, especially among adolescents because they experience a range of emotional, social and physical changes. The effects of mental illnesses on adolescents vary and can be acute, chronic, mild or severe. The commonest mental illnesses among adolescents are depression and anxiety disorders. Adolescents living with HIV have additional risk factors that increase their susceptibility to mental illnesses. This increased vulnerability may result from the loss of family, having to live independently, with relatives or in care. They are often exposed to poverty and violence. The stigma, discrimination, and social isolation that is associated with HIV further impact mental health negatively. They may result in poor adherence to ART (8).

The General Health Questionnaire (GHQ) 12 will be used to assess the mental health status in this study. The GHQ which was developed in 1970 by Goldberg to measure the current mental health has since been used in different settings and different cultures (42). The questionnaire was originally developed as a 60-item instrument but many shorter versions have been developed over time. The GHQ-12 is brief, simple, easy to complete, and has been widely used in research settings as a screening tool. It is a consistent and reliable instrument when used in the general population (42, 43).

Process measures

An ART adherence checklist will be completed by the counselors during each counseling session. The filled checklists will be examined to monitor the adequacy of counseling sessions. The participants will be required to send a reply SMS as soon as possible after ART and follow-up reminders are received. This will help confirm that SMS are delivered to participants and serve as a measure of feasibility and acceptability of the intervention.

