ART adherence will be measured at baseline and at every follow-up visit. Complete case analysis and the intention-to-treat analysis will be carried out. Baseline characteristics will be compared using the chi-square test, rank-sum test, and independent t-test as appropriate. The proportion of participants who are adherent to ART [$\geq 95\%$] at the end of the follow-up period will be compared with the baseline data using the chi-square test. The independent t-test will be used to compare the means of ART adherence between the investigation and control groups after each follow-up visit in order to test if the intervention has any effect. The incidence proportion, incidence rate, relative risk, risk difference, and odds ratio will be used to measure the effect. Multiple regression analyses will be used to control for possible confounders. Subgroup analysis will also be undertaken in order to generate further hypotheses. Survival analysis will also be carried out to adjust for

censoring (competing risk and loss to follow-up). Longitudinal data analysis will be carried out to explore the change in response over time.

The acceptability of the SMS will be accessed by the responses given by participants. The proportion of participants who find the method acceptable will be determined.

The feasibility will be determined using the proportion of participants who are deemed to have completed the study (participate fully).

The study will also assess client satisfaction and the possible effect of adherence on mental health status of adolescents. Correlation and linear regression analyses will be used to determine the association between adherence (percent) and mental health status (GHQ 12 measure).

PROJECT ACTIVITIES AND IMPLEMENTATION

Figure 1 shows a synopsis of the intended activities, RCT design the overall flow during the study.

Timeline

Activity	Period (week)
Initial Planning, Procurement, recruitment and training of project staff	1 to 13
Review meetings	Monthly
Recruitment of participants and informed consent	9 to 21
Randomization and baseline activities	22 to 25
Data cleaning, entry and analysis	9 to 52
Follow-up	26 to 45
Report writing and rounding up	45 to 52

Project management/logistics support

Staffing

For effective project implementation and management, the following staff would be required:

Role		% time	Responsibilities
Principal Investigator	1	25%	Oversees entire project, especially its scientific integrity

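### Mental health status (GHQ-12) is a secondary outcome, but its only stated analysis is its association with adherence; no between-arm comparison is planned and its timing is not given

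*Combined protocol and SAP*

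**What the plan says.** Under Expected Outcomes, the list headed "Secondary outcome measures" has two items: patient satisfaction and mental health status. For the second, the protocol says: "The General Health Questionnaire (GHQ) 12 will be used to assess the mental health status in this study". It gives no visit, scoring method or summary measure.

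Statistical Methods states the question as "the possible effect of adherence on mental health status of adolescents" and then gives the method: "Correlation and linear regression analyses will be used to determine the association between adherence (percent) and mental health status (GHQ 12 measure". No term for randomised arm is mentioned. The between-arm test in that section is for adherence: "The independent t-test will be used to compare the means of ART adherence between the investigation and control groups after each follow-up visit". The sentences on multiple regression, subgroups, survival and longitudinal analysis are general and do not name GHQ-12.

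On timing, the Follow-up section says: "ART adherence and client satisfaction will be assessed at each follow-up visit". It adds viral load at baseline and week 20. The opening summary and the five numbered items under Baseline activities cover socio-demographics, risk behaviour, alcohol and drug use, client satisfaction and adherence. Neither names GHQ-12.

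The Intervention section provides that every participant, in either arm, also receives a clinic-based intervention intended to improve mental status.

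**The concern.** A secondary outcome of a randomised trial would normally be compared between the randomised groups. Here it is related only to percent adherence, which is not randomised and is measured after allocation. Adolescents who adhere better may differ from the others in many ways that also bear on GHQ-12.

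The direction is also unsettled within the document. Statistical Methods speaks of adherence possibly affecting mental health. The mental health paragraph under the secondary outcomes argues the other way; of the pressures it describes on adolescents with HIV, it says: "They may result in poor adherence to ART (8". Hypothesis c likewise treats psychosocial factors as predictors of adherence. A correlation, or a regression on adherence alone, cannot tell these directions apart.

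At stake is what can be reported for this outcome. As planned, a report could give an adherence–GHQ-12 coefficient but no estimate of what the reminders did to mental health. If GHQ-12 is not taken at baseline, that value cannot be obtained later, and adjustment for it is lost.

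**Working it through.** The documents give no GHQ-12 figure (no SD, target difference or power), so there is none to reproduce. The stated 96 per group concerns adherence and plays no part here.

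**Text check**

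| Question | Where checked | Finding |
|---|---|---|
| Is it an outcome? | Secondary outcome measures | Yes, item 2 of 2 |
| Is a between-arm analysis stated? | Statistical Methods | For adherence only |
| Is it in the baseline lists? | Opening summary; Baseline activities, items 1–5 | No |
| Is it in the follow-up list? | Follow-up | No |
| Is the other secondary outcome in those lists? | Same places | Yes, client satisfaction is in both |

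The last row matters: the lists do include a secondary outcome, so the omission is particular to GHQ-12.

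Because both arms receive the mental health intervention, a change from baseline within an arm would mix its effect with that of SMS and with time. The difference between arms removes what the arms share.

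**What an arm comparison could detect**

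Inputs: 200 participants randomised 1:1, so 100 per arm; 10% attrition (the sample-size assumption), so 100 × 0.90 = 90 per arm. Assumed: two-sided alpha 0.05 (the documents state none), 80% power, differences in SD units.

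- Unadjusted: (1.96 + 0.842) × √(2/90) = 2.802 × 0.1491 = 0.418 SD. With 100 per arm: 2.802 × √(2/100) = 0.396 SD.
- Adjusted for a baseline value with correlation r: 0.418 × √(1 − r²). The documents do not give r, so a range is shown:
  - r = 0.3: 0.418 × √0.91 = 0.40 SD
  - r = 0.5: 0.418 × √0.75 = 0.36 SD
  - r = 0.7: 0.418 × √0.51 = 0.30 SD
- Unadjusted power with 90 per arm is about 27% for 0.2 SD, 52% for 0.3, 77% for 0.4 and 92% for 0.5.

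**Do the two analyses answer the same question?**

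A simulation illustrates this (3,000 runs, 90 per arm, all effect values assumed). SMS raises adherence by 0.4 SD throughout. Entries are the share of runs with p < 0.05.

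| Assumed truth | Adherence–GHQ-12 correlation | Arm t-test |
|---|---|---|
| No SMS effect on GHQ-12; shared cause gives a correlation of size 0.3 | 98% | 6% |
| SMS improves GHQ-12 by 0.5 SD, not through adherence; no shared cause | 10% | 92% |

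The correlation can be clearly significant when SMS does nothing to GHQ-12, and mostly silent when SMS has a moderate effect.

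**The case against.** The strongest reply is that the plan never asks whether SMS changes mental health. Objective 1 and hypothesis a concern adherence; objective 3 and hypothesis c concern predictors of adherence. Statistical Methods poses an adherence question about mental health and supplies an analysis to match. On this view the fault is one of labelling, and calling GHQ-12 exploratory would cure it at no cost. This stands as far as the remedy goes: relabelling is acceptable. It does not justify keeping the secondary-outcome label with no randomised comparison.

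Three stronger readings are tempting, and the documents do not support them.

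- **That GHQ-12 will not be collected.** The outcome section commits to using it. Figure 1, described as a synopsis of activities, is not shown and may contain it. The evaluation text mentions pre- and post-test data without naming measures. What is established is that the visible text does not state the timing.
- **That the randomised comparison is lost for good.** If GHQ-12 is taken at a follow-up visit, an unadjusted comparison of arms is valid without a baseline value, and the Data Analysis section provides for analysts to receive the participants in two coded groups. The comparison would be unplanned and less precise, but possible.
- **That the plan presents a confounded association as an established effect.** The wording is a possible effect in one sentence and an association in the next. It is loose rather than a causal claim.

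It is also fair that the detectable differences show what an added test could achieve, not the harm done by omitting it, and that such a test would be weak for small effects.

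**Conclusion.** The point holds as a mismatch between label and analysis, together with an unstated measurement time. As written, the plan yields no estimate of the SMS effect on a named secondary outcome, and the analysis it does state cannot separate cause from consequence or remove confounding. A reader might infer that the trial can never answer the question. That goes too far, because a follow-up GHQ-12 could still be compared by arm.

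On the assumptions above, the cost of lacking a baseline value is one of precision: a detectable difference of about 0.42 SD instead of 0.36 SD at r = 0.5, or instead of 0.40 to 0.30 SD over r = 0.3 to 0.7. The conclusion about the text rests on none of these figures. The primary adherence conclusion is unaffected. The correction should be made, ideally before baseline data are collected.

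**What to change.** 1. Add GHQ-12 to the baseline questionnaire and to the week-20 visit, and state how it is scored.
2. In Statistical Methods, compare week-20 GHQ-12 between arms by linear regression on randomised arm and baseline GHQ-12, reporting the difference with its confidence interval.
3. Keep the adherence–GHQ-12 correlation and regression, labelled exploratory, and describe them as an association rather than a possible effect of adherence.
4. If no arm comparison is wanted, move mental health out of the secondary outcomes and call it an exploratory correlate.

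Cost of items 1 to 3: a 12-item form at two existing visits (a few minutes per participant each time) and one more regression. The comparison will have low power for small effects, about 27% for 0.2 SD unadjusted, so a null result should be read from its confidence interval. Item 4 costs only a wording change, but leaves the SMS effect on mental health outside the plan.

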For the purpose of this study, we defined poor adherence as self-reported < 95% adherence in the preceding one month using a validated visual analogue scale (25, 26). Self-reported 95% adherence level is an ideal cut-off point because self-reported measures tend to exaggerate adherence and such high adherence level will minimize the occurrence of false-negatives (27). Adolescents who are too ill to require hospital admission will be excluded from the study.

Initial eligibility screening and recruitment will be carried out by the primary caregivers using a checklist. Potential participants who meet the first four criteria will be presented with a visual analogue scale (VAS) labelled 0 to 100% at intervals of 5%. They will be educated on the implication of various percentages e.g. 0%, 50%, and 100%. They will be required to put a mark on the line at the point that shows their best guess about how much of their prescribed ART medication they had taken in the preceding one month (4 weeks). Volunteers who choose points less than 95% mark will be regarded as being non-adherent to ART and will be eligible to participate in the study. Eligible and willing participants will then be referred to the research assistants for a comprehensive informed consent process.

Baseline activities

At the baseline, the research assistants will give the volunteer participants a detailed explanation of the study, including its aim, duration, intervention and possible benefits. All the volunteers will be required to give a signed informed consent in a private room. Adolescents aged 15 to 19 years are thought to be relatively mature. According to a brief of AIDS regulations and Laws in Nigeria, children who are deemed mature in this context are capable of giving informed consent (28). Besides, based on evidence from South Africa and Lesotho, the WHO recommended that the legal age of consent for HIV testing and treatment should be 12 years (29). The consenting volunteers will then be allocated unique identifiers that they will maintain throughout the course of the study. The contact details of the lead investigator will be made available to the participants so that he can be reached directly for any reason that is related to the study. Baseline data will be obtained in a private room by trained research assistants using structured interviewer-administered paper-based questionnaires over a period of about 40 minutes. The questionnaire will assess:

1. Socio-demographic variables.

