HIV viral load estimation will be done in line with APIN Public Health initiative program and in accordance with the national guideline. Sample collection, handling and disposal follows the standards and guidelines outlined by the WHO and PEPFAR (36, 37). The participants' capability to operate mobile phones will be enhanced. The research assistants will work with participants to select from a list the most preferred SMS that will serve as a daily reminder of ART adherence. Each participant will select an SMS format that will serve as a reminder for follow-up visit reminders. In addition, the participants will also choose the preferred language and time for SMS reminders. The participants will receive the adherence counseling by trained counselors. The messages will be designed in such a way that they are sensitive and protect the privacy of the participants. The participants will be able to contact the lead investigator if they wish to change their chosen messages or if the services to their mobile phones are disrupted.

Randomization

The Project will collaborate with an accredited medical internet technology solutions firm (Golden Business Resource Limited) to set up a database system for dissemination and receipt of SMS. Following baseline

activities, the participants will be randomly allocated to intervention and control groups by the database administrator. Random allocation will be achieved through a computer-generated simple randomization scheme. The investigators, data manager, research assistants, counselors and other project staff will be blinded throughout the study.

Intervention

All the participants will receive one SMS reminder each for follow-up appointments 48 hours and 24 hours before the follow-up visit date. The participants that are allocated to the intervention group will also receive daily ART adherence reminder SMS. Participants in the intervention group will be required to send reply SMS to their daily messages as soon as possible. They will be expected to send '1' if they find the reminder acceptable depending on the circumstance around them at the time the message is received. They will be expected to send '2' if it was not so acceptable.

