The study will be evaluated in a participatory manner using both process and outcome indicators. This will be carried out midterm into the project, and at the end of the project. A data analyst will be engaged to participate in the analysis of pre and posttest data and evaluation workshop involving the investigators and all project staff.

Sustainability of Interventions

The most problematic aspects regarding the sustainability of many projects, especially those involving elements of service in this scenario, are recurrent costs of accommodation, consumables such as drugs, staff salaries etc. With this in mind, the project will engender the commitment of all relevant stakeholders including the State Government, relevant LGA authorities, community leaders including the Traditional and Religious Leaders. The Ogun SACA, being an implementing partner, will be involved at all stages of planning, implementation, and evaluation.

The Ogun State HIV control program does not have a PCR DNA machine for viral load testing. However, there is an arrangement with some tertiary facilities (about 100 to 160 km from the project site) to which samples are transported for analysis. This mitigates the cost of having to purchase a viral load machine by about 90%.

The database system for dissemination and receipt of SMS which will be put in place by this study will also be available for the scale up of the intervention if it is proved to be feasible and effective. Also, the core intervention (SMS reminders) is relatively cheap and will, therefore, be easy to sustain.

Dissemination of findings

The findings of the study will be communicated to the funding agency as agreed. The findings will also be submitted to relevant governmental agencies. The findings of the study will be presented as two abstracts at the International AIDS Society conference 2019 and five (5) publications in relevant reputable journals, including AIDS and Behaviour, Journal of Adolescent Health, and International Journal of Adolescent Medicine and Health.

Limitations of the study

The inclusion criteria set the adherence level at a very high level (95%). It is possible that this will mitigate the effect of the tendency of individuals to exaggerate their self-reported adherence to medications.

FUNDING/SPONSORSHIP

STARTA Trials (Adolescents) will be undertaken with a grant provided by Merck Sharp and Dohme (MSD) under the Merck Investigator Studies Program-2017.

INVESTIGATORS

Institution

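### Self-reported adherence may be over-reported more in the arm that knows it gets daily reminders; the 95% entry level cannot correct this, and the plan has no rule for disagreement with the objective measures

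*Combined protocol and SAP*

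**What the plan says.** The plan accepts that self-report is inflated and answers with a high entry level. Under Participants' recruitment: "Self-reported 95% adherence level is an ideal cut-off point because self-reported measures tend to exaggerate adherence". Entry uses that level: "we defined poor adherence as self-reported < 95% adherence in the preceding one month using a validated visual analogue scale". The Limitations section returns to the 95% level in the inclusion criteria and adds: "It is possible that this will mitigate the effect of the tendency of individuals to exaggerate their self-reported adherence to medications".

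The primary outcome is ART adherence, measured by "visual analog scale (VAS), Viral load, Pill count, Pharmacy record" and the ACTG questionnaire. Two of these five are self-report (VAS and ACTG). The VAS is the only one the outcome section argues for: "The VAS has been found to be reliable, valid and suited for patients in resource-limited settings", and "It showed the highest sensitivity to detect patients with possible virologic failure at 95% cut-off for non-adherence".

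The Randomization and Data Analysis sections list investigators and project staff as blinded; participants are not on the list. Under Intervention: "The participants that are allocated to the intervention group will also receive daily ART adherence reminder SMS". That arm must also reply to each daily message.

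Statistical Methods compares the proportion at or above 95% at the end of follow-up with baseline by chi-square, and mean adherence between arms by t-test after each visit. It also lists risk difference, relative risk and odds ratio. It does not name the instrument behind the 95% outcome or the mean, or say how disagreement between instruments is handled.

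**The concern.** Participants know whether they receive daily messages. The reminder text is chosen at baseline, before randomization, so control participants can also notice that it never arrives. Consent explains the aim and the intervention. Those who are reminded daily to take ART, and who answer each reminder, may feel more pressure to report having taken it. Blinding the staff limits interviewer influence but not this, because the participant makes the mark.

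A high entry level deals with a different problem: at screening it catches people who mildly overstate their adherence. Everyone then enters below 95% on the VAS and counts as adherent at 95% or above. On a scale labelled every 5%, someone who marked 90% at entry crosses by marking one step higher. If one arm is readier to take that step, the excess looks like a treatment effect. At stake is whether a positive self-report result can be read as better adherence.

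**Working it through.** **The plan's own figure.** The stated size is 96 per group for a 20-point difference from 49% with 80% power and 10% attrition. Significance level and sidedness are not stated; I assume two-sided 5%. With the pooled-variance formula for 49% against 69%, n = 93.7, so 94 per group, and 94/0.90 = 104.4, so 105 after attrition. The stated 96 is close to the figure without attrition. This does not affect the present point.

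**What a common cut-off does.** Let p be the true adherent proportion in both arms (no effect), g the share of truly non-adherent participants who over-report across 95% in both arms, and f the further share who do so only in the intervention arm.

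- Control, reported: p + (1 − p)g
- Intervention, reported: p + (1 − p)(g + f)
- False difference: D = (1 − p)f

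Common over-reporting g cancels; f passes straight into the difference. Moving the cut-off could change f but does not make the arms equal.

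**Illustration.** Inputs from the plan: 200 participants at 1:1 is 100 per arm; less 10% attrition, n = 90. The 49% is the plan's assumed adherent proportion. Assumptions of mine: g = 0, the values of f, two-sided 5%, and a two-proportion comparison.

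With p1 = p, p2 = p + D and p̄ their mean, s0 = √(2p̄(1 − p̄)/n) and s1 = √((p1(1 − p1) + p2(1 − p2))/n). The chance of rejection is Φ((D − 1.96·s0)/s1) + Φ((−D − 1.96·s0)/s1).

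For p = 0.49 and f = 0.20: D = 0.51 × 0.20 = 0.102, p2 = 0.592, s0 = 0.0743, s1 = 0.0739. The first term is Φ((0.102 − 0.1456)/0.0739) = Φ(−0.59) = 0.278; the second is below 0.001.

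| True p | f = 10%: D, rejection | f = 20%: D, rejection | f = 30%: D, rejection |
|---|---|---|---|
| 0.49 | 5.1 points, 10.5% | 10.2 points, 27.8% | 15.3 points, 54.5% |
| 0.30 | 7.0 points, 16.8% | 14.0 points, 49.4% | 21.0 points, 82.4% |
| 0.20 | 8.0 points, 24.1% | 16.0 points, 66.9% | 24.0 points, 93.9% |

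With f = 0 the rate is 5%. The lower rows matter because the sample is selected for poor adherence. The f that would reproduce the whole 20-point design difference is 0.20/(1 − p): 39% at p = 0.49, 29% at 0.30, 25% at 0.20.

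**The t-test on means.** No cut-off enters it. A reporting shift of 5 VAS points (one scale interval) in one arm has standard error SD·√(2/90). For assumed SDs of 10, 15, 20 and 25 this is 1.49, 2.24, 2.98 and 3.73, and the chance of a significant result favouring SMS, Φ(5/SE − 1.96), is 92%, 61%, 39% and 27%.

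**The chi-square against baseline.** If the VAS is the instrument, the baseline proportion is 0% by the entry rule, so this test cannot separate a reminder effect from over-reporting or any other change over time.

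**The case against.** The strongest reply is that the plan does not rest on self-report. Three of the five primary measures are viral load, pill count and pharmacy record, and blinded research assistants do the pill counts and obtain the pharmacy records. That stands. A reader might infer that the 95% level is the plan's only protection, or that the VAS is the primary endpoint; the documents support neither. The Limitations sentence is a hedged remark about entry and claims nothing about comparing arms. Statistical Methods names no instrument.

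Both arms also get counselling at every visit, appointment SMS and the same payment, so both are under some pressure to report well. A stronger motive in the intervention arm is a judgement, plausible because of the daily messages and replies, but not shown.

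The illustration has limits too. The values of f have no source in the documents. The 49% appears in the Background as a viral suppression rate. The false-positive figures are for a between-arm test of proportions, which Statistical Methods does not explicitly name, although it lists the risk difference and the sample size is set on a difference in proportions.

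What remains is that collecting objective measures protects the conclusion only if the plan says how they bear on it, and it does not.

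**Conclusion.** The point holds in a limited form. VAS and ACTG comparisons are open to over-reporting that differs by arm; neither the 95% level nor the t-test on means removes it; and no rule covers a positive self-report result beside flat objective measures. Hypothesis (a) could then be declared supported on the VAS alone.

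The size is unknown. The figures above show sensitivity under assumed over-reporting, no true effect and 90 per arm; they are not estimates of this trial's error rate. A reader might go further and conclude that the trial will produce a false positive, or that its adherence result cannot be trusted. The documents do not support that: they give no evidence on the amount of differential over-reporting, and the data needed to detect it are already planned. This is a change the sponsor should make, mainly to analysis and wording.

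**What to change.** 1. **Limitations of the study:** state that the 95% entry level does not protect the between-arm comparison from over-reporting related to arm.
2. **Statistical Methods:** report the between-arm difference with its confidence interval for VAS, pill count and week-20 viral load side by side. Describe a result seen only on VAS or ACTG as improved self-reported adherence. Let any claim of improved adherence rest on the estimate and interval of an objective measure. Agreement in direction is not enough: with no true effect, pill count and viral load would both favour the intervention by chance about 25% of the time if independent (0.5 × 0.5) and up to 50% if fully correlated. Pill count depends on what participants bring back and may share some of the motive, so viral load is the better-insulated check.
3. **Discordance table:** give, by arm, the proportion with VAS at or above 95% but pill count below 95% or an unsuppressed week-20 viral load. Use the suppression threshold of the national guideline that the plan already follows, and state it.
4. **Viral load schedule:** reconcile the Follow-up section (baseline and week 20) with the primary outcome section, which lists it among measures taken at every visit.

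The cost is wording, one set of estimates and one cross-tabulation; no new data are needed. The downside is a more guarded claim if only self-report improves.
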